## Summary of the Clinical Trial Protocol and Statistical Plan

Name of Sponsor/Company:	AiCuris Anti-infective Cures GmbH	
Title of the trial: A randomized, double-blind, multi-center, three arm (pritelivir, placebo and Zovirax ® ) parallel group, comparative trial to assess the efficacy and safety of pritelivir 5% w/w ointment for the treatment of recurrent herpes labialis in adults – LipP 1		
Trial center(s): 10 to 14 investigational sites in the US		
Planned study period (years): First Subject First Visit: 4 th quarter 2016 Last Subject Last Visit: 3 rd quarter 2017	Phase of development: 2	
Objectives: To assess the efficacy, tolerability and safety of pritelivir 5% w/w ointment applied 5 times daily for 4 days for the treatment of recurrent herpes labialis (rHL) in adults		
Trial design: This is a randomized, double-blind, multi-center, three arm parallel group, comparative trial to assess the safety and efficacy, ie, proportion of subjects with non-ulcerative lesions, in adult subjects with rHL treated with pritelivir 5% w/w ointment. The statistical superiority will be tested against placebo and a descriptive comparison with Zovirax ® Cream will be made. The start of treatment with trial medication will be initiated by the subject within one hour of noticing the first sign or symptom (eg, prodrome) of a recurrence of herpes labialis (HL). Trial medication will be applied to the affected area 5 times daily for 4 days.		
Number of subjects (planned): approx. 360 subjects should be enrolled resulting in at least 71 subjects dosed in each treatment arm.		

Diagnosis and main criteria for inclusion:
 
 
1. Healthy men and women of any ethnic group aged <math>\geq 18</math> years ;
 
2. Subjects should have experienced <math>\geq 4</math> recurrences of HL in the previous 12-month period;
 
3. Subjects should have experienced prodromal symptoms in at least 50% of rHL episodes and should have developed ulcerative lesions that have progressed through vesicle, ulcer, and crust stages in at least 50% of the episodes;
 
4. Willingness not to use any topical application (such as cosmetics, lip balm, sunscreens etc.) other than the trial medication in the area of lesion development from start of prodromal symptoms to healing;
 
5. Willingness not to use any systemic and topical anti-HSV agent during the trial participation including prescription and over-the-counter products,
 
6. Willingness not to use any systemic, anti-inflammatory or analgesic agents from start of prodromal symptoms to healing;
 
7. Willingness to refrain from mechanical disruption (ie, scrubbing, lancing, shaving) of the prodromal area or lesion after start of treatment with trial medication until end of the trial participation;
 
8. Women of child bearing potential and males must use adequate contraception;
 
9. Subject must give written informed consent.
 
10. Subjects with current lesion may be enrolled, but must not to treat the lesion present at randomization with the trial medication; they should be instructed to wait for the next subsequent lesion.
 
		

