**Diagnosis and main criteria for exclusion:**

1. Known intolerance to pritelivir or any of the ointment ingredients (ie, butylated hydroxytoluene (BHT), PEG-400, PEG-4000, propylene glycol);
2. Known intolerance to Zovirax® Cream or any of the ingredients (ie, acyclovir, cetostearyl alcohol, mineral oil, poloxamer 407, propylene glycol, sodium lauryl sulfate, and white petrolatum) or valacyclovir;
3. Any skin conditions that could interfere with the assessment of HL recurrences (eg, eczema, psoriasis, acne);
4. Any other condition which in the opinion of the Investigator would interfere with successful completion of this clinical trial;
5. Pregnant and/or breastfeeding women;
6. Participation in any investigational drug trial within the last 30 days before randomization for this clinical trial;
7. Previous treatment with pritelivir tablets;
8. Previous participation in a HSV vaccination trial (unless having received placebo);
9. Clinically relevant ECG abnormalities (eg, QTc according to Fridericia: QTcF > 450ms for males and QTcF > 470ms for females; PR > 220 ms) at screening;
10. Clinically relevant abnormalities in laboratory indices at screening which in the opinion of the investigator might have an impact on the safety and evaluability of the subject;
11. Known chronic infections which in the opinion of the investigator might have an impact on the safety and evaluability of the subject;
12. Evidence of active malignancy or immunodeficiency disease, or require chronic use of immunosuppressive drugs (eg, systemic steroids) or topical steroids, or chronically use antiviral medication with activity against HSV;
13. HIV positive based on screening labs.

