**Test product, dose and mode of administration**

Pritelivir 5% w/w ointment, 5 times daily, topical application.

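### Does the double-blind label need correcting when the active comparator is a cream and the other two products are ointments?

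*Combined protocol and SAP*

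**What the plan says.** The title describes the trial as "A randomized, double-blind, multi-center, three arm (pritelivir, placebo and Zovirax" and so places the cream arm under the blinding label by name. The trial design paragraph repeats the label: "This is a randomized, double-blind, multi-center, three arm parallel group, comparative trial". The same paragraph gives the two comparisons different roles: superiority is tested against placebo, while against the active comparator there is only "a descriptive comparison with Zovirax". The sample size section repeats that the Zovirax comparison is descriptive.

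The test product is given as "Pritelivir 5% w/w ointment, 5 times daily, topical application". The reference therapy section lists a placebo ointment and Zovirax Cream on the same five-times-daily schedule. Exclusion criteria 1 and 2 name the ingredients: for the ointment, "butylated hydroxytoluene (BHT), PEG-400, PEG-4000, propylene glycol"; for the cream, "acyclovir, cetostearyl alcohol, mineral oil, poloxamer 407, propylene glycol, sodium lauryl sulfate, and white petrolatum".

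Lesion stage and lesion area are assessed daily by the Investigator (efficacy measurements). Subjects record pain, lesion stage and tenderness in a diary, which site staff review at each visit (subject diary documentation).

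**The concern.** An ointment and a cream are different dosage forms, and the only placebo listed is an ointment. Without a placebo cream for a double-dummy scheme, or disguised containers, a reader cannot see how a subject given the cream stays unaware of it. Inclusion criterion 4 bars other topical products at the lesion, so a dummy would have to be part of the trial medication, and none is listed.

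The population makes recognition plausible. Subjects must have had at least four "recurrences of HL in the previous 12-month period", and exclusion 12 removes those who "chronically use antiviral medication with activity against HSV" but not those who have used Zovirax Cream now and then.

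At stake is how much weight the Zovirax comparison can carry. If subjects recognise the product, self-reported pain and tenderness could partly reflect that knowledge, yet the results would be presented as double-blind. One third of the planned evaluable recurrences sit in that arm.

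**Working it through.** **1. Do the listed products differ?** Leaving the actives aside, the ointment has 4 listed ingredients (BHT, PEG-400, PEG-4000, propylene glycol). The cream has 6 (cetostearyl alcohol, mineral oil, poloxamer 407, propylene glycol, sodium lauryl sulfate, white petrolatum). One, propylene glycol, is common to both. So 4 − 1 = 3 ointment ingredients and 6 − 1 = 5 cream ingredients are not shared. The formulations differ, but an ingredient list does not show that a subject can tell which product was dispensed. The document gives no colour, texture, odour or container. In a parallel-group trial each subject is assigned one product, so no side-by-side comparison arises.

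**2. Does the document contradict the label?** Compare what it says about masking, arm by arm:

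- Pritelivir ointment: no masking method described.
- Placebo ointment: none described. That it matches the active ointment in look and feel is inferred from its name.
- Zovirax Cream: none described, and the dosage form differs.

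No arm is called open. The silence covers all three arms, in a document headed as a summary. The product sections give dose and mode of administration, where packaging and dispensing would not normally be described. The exclusion list is headed as the main criteria only, so silence on occasional past use is weak evidence too.

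**3. Which results could be touched?** The seven secondary endpoints divide as follows:

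- wholly subject-reported: pain rate, pain duration, pain severity, tenderness duration (4);
- partly symptom-dependent: duration of episode, in non-vesicular lesions whose symptoms outlast the return to normal skin (1);
- based on the Investigator's lesion-area measurement: maximum and cumulative area (2).

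4 + 1 + 2 = 7. The Zovirax arm holds 213 / 3 = 71 of the planned evaluable recurrences.

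**4. Is the powered comparison touched?** Reproduce the plan's figure with p1 = 0.26, p2 = 0.50, two-sided 5%, 80% power (the plan does not state sidedness) and mean proportion 0.38:

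n = [1.960 × √(2 × 0.38 × 0.62) + 0.842 × √(0.26 × 0.74 + 0.50 × 0.50)]² / 0.24² = (1.345 + 0.560)² / 0.0576 ≈ 63.0, rounded up to 64 per arm.

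With continuity correction: (63.0 / 4) × [1 + √(1 + 4 / (63.0 × 0.24))]² ≈ 71.1, which is 72 rounded up or 71 to the nearest whole number. The plan has 71. Exact two-sided Fisher power at 71 per arm is 79.8%. For the total, 213 / (1 − 0.40) = 355, against 360 planned.

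No input to these figures involves the Zovirax arm's blinding. A subject who recognises an ointment can rule out Zovirax, but dosage form alone does not separate pritelivir from placebo. That knowledge is equally available in both ointment arms, so it gives no reason to expect a difference between them.

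**The case for a change.** The strongest case for a change is that the label is unqualified, the title names Zovirax, and nothing in the document supports blinding of that arm. A descriptive result presented as double-blind carries more weight than one that is not, and a third of the evaluable recurrences serve this comparison. Lesion stage is also recorded by both the Investigator and the subject without a statement of which record governs, so the Zovirax comparison on the primary endpoint might be exposed as well. A remedy would cost a sentence, or a few words in the title and table labels.

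Part of this stands. The dosage forms differ, no masking method is given, and a reader would be better served by knowing how the cream is disguised and from whom. But lack of support in a summary is not evidence that the label is false. Narrowing it to pritelivir versus placebo would assert that the cream arm is unmasked, which the document does not say. Relying on Investigator staging would add little: the plan already has the Investigator stage lesions daily, and if the cream were unmasked nothing shows that the Investigator would stay blind, since site staff review the diaries at each visit.

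**Conclusion.** The observation is accurate, but no change to the plan follows. It is a detail missing from a summary. If a masking method exists, stating it records what is already done. If none exists, the consequence is a qualifying phrase when the Zovirax results are reported, which an analyst would add to a comparison already labelled descriptive.

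The reach is limited to that comparison, with 71 of 213 planned evaluable recurrences in the Zovirax arm, and mainly to four of seven secondary endpoints. The duration-of-episode endpoint is exposed only in a subset whose size the document does not allow one to estimate. The effect on the sample size is nil. The effect on the superiority test is also nil, provided the placebo ointment matches the active ointment, as its name implies but the document does not state.

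The conclusion would be different if the full protocol showed the cream arm to be open, or if an inferential claim against Zovirax were planned. The document shows neither.

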**Diagnosis and main criteria for exclusion:**

1. Known intolerance to pritelivir or any of the ointment ingredients (ie, butylated hydroxytoluene (BHT), PEG-400, PEG-4000, propylene glycol);
2. Known intolerance to Zovirax® Cream or any of the ingredients (ie, acyclovir, cetostearyl alcohol, mineral oil, poloxamer 407, propylene glycol, sodium lauryl sulfate, and white petrolatum) or valacyclovir;
3. Any skin conditions that could interfere with the assessment of HL recurrences (eg, eczema, psoriasis, acne);
4. Any other condition which in the opinion of the Investigator would interfere with successful completion of this clinical trial;
5. Pregnant and/or breastfeeding women;
6. Participation in any investigational drug trial within the last 30 days before randomization for this clinical trial;
7. Previous treatment with pritelivir tablets;
8. Previous participation in a HSV vaccination trial (unless having received placebo);
9. Clinically relevant ECG abnormalities (eg, QTc according to Fridericia: QTcF > 450ms for males and QTcF > 470ms for females; PR > 220 ms) at screening;
10. Clinically relevant abnormalities in laboratory indices at screening which in the opinion of the investigator might have an impact on the safety and evaluability of the subject;
11. Known chronic infections which in the opinion of the investigator might have an impact on the safety and evaluability of the subject;
12. Evidence of active malignancy or immunodeficiency disease, or require chronic use of immunosuppressive drugs (eg, systemic steroids) or topical steroids, or chronically use antiviral medication with activity against HSV;
13. HIV positive based on screening labs.

**Test product, dose and mode of administration**

Pritelivir 5% w/w ointment, 5 times daily, topical application.

**Duration of Treatment:**

Four days (20 applications).

**Reference therapy, dose and mode of administration**

Pritelivir placebo ointment, 5 times daily, topical application

Zovirax® Cream, 5 times daily, topical application.

**Criteria for evaluation:**

**Efficacy:**

[figure not shown]
Primary endpoint:

- The percentage of subjects with non-ulcerative lesions in each treatment group.

Secondary endpoints:

- Duration of lesion episode (DOE), defined as time from treatment initiation to the healing of the primary lesion (loss of crust) for subjects who experienced a vesicular lesion. For subjects whose primary lesions were not vesicular in nature, DOE is the time from the treatment initiation to the return to normal skin or to the cessation of symptoms, whichever occurs last;
- Pain rate, defined as number of days with pain at lesion site relative to the total number of days with analyzable pain through daily subject self-assessment;

- Subject-assessed duration of lesion pain, defined as the time from first dose of trial medication until pain is no longer reported by the subject (date and time);
- Subject-assessed severity of lesion pain defined as the average daily NUMERICAL RATING SCALE (NRS) pain score using a single-dimensional scale assessing pain intensity at lesion site, 11 intensities [no pain (0) to worst pain imaginable (10)];

- Maximum lesion area (length x width) for ulcerative lesions during the vesicular, ulcerative and hard crust stages;
- Cumulative lesion area (sum of daily maximum lesion areas);
- Duration of lesion tenderness (unpleasantness upon touching the affected area).

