**Subject diary documentation:**

Subjects will document the following in their diary:

1. Time of each application of trial treatment,
2. Pain intensity, changes in pain intensity, and cessation of pain at each application of trial treatment (at the first and last daily application as a minimum),
3. Pain intensity, changes in pain intensity, and cessation of pain in the morning and evening on days after stop of application of trial treatment until pain disappeared,
4. Lesion stage at each application of trial treatment,
5. Lesion stage in the morning and evening on days after stop of application of trial treatment until lesion healing,
6. Lesion tenderness at each application of trial treatment, and,
7. Lesion tenderness in the morning and evening on days after stop of application of trial treatment until lesion tenderness disappeared.

Subject diaries will be reviewed by the investigational site staff at each visit.

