**Safety measurements:**

The following safety measures will be performed at screening and at Visit 5 (Day 5/6) and at the End of Trial Visit (Day 12±1) after initiation of treatment:

1. Safety laboratory parameters, ie, serum chemistry, hematology, coagulation and urinalysis
2. Vital signs, ie, systolic and diastolic blood pressure, pulse rate
3. Standard 12-lead electrocardiogram (ECG) according to Einthoven, Goldberger and Wilson
4. Physical examination including the assessment of the skin, head, eyes, ears, nose, neck, lymph nodes, throat, and extremities, and the following body systems: musculoskeletal, cardiovascular, respiratory, gastrointestinal and neurological.

Any other clinically relevant findings will be recorded.

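### Pain rate has no common window and its diary denominator ends with the pain, so it is nearly flat in duration for pain present from Day 1 and can rank subjects in the wrong order

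*Combined protocol and SAP*

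**What the plan says.** Under Criteria for evaluation, the secondary endpoints include "Pain rate, defined as number of days with pain at lesion site relative to the total number of days with analyzable pain", taken from the subject's daily self-assessment. The section does not define an analyzable day and gives no window common to all subjects.

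The denominator therefore rests on what the diary collects. Under Subject diary documentation, pain is recorded on every dosing day, at least at the first and last application. After dosing, item 3 asks for pain intensity, its changes and "cessation of pain in the morning and evening on days after stop of application of trial treatment until pain disappeared". Duration of Treatment gives "Four days (20 applications". Under Trial design, the subject starts treatment "within one hour of noticing the first sign or symptom (eg, prodrome) of a recurrence". The lesion stages under Methodology list itching and tingling beside pain as prodromal symptoms, so the first diary days need not be painful.

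Two other pain endpoints are listed separately: a duration, measured from first dose "until pain is no longer reported by the subject (date and time"), and "Subject-assessed severity of lesion pain defined as the average daily NUMERICAL RATING SCALE (NRS) pain score".

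**The concern.** A rate needs a denominator that does not depend on the outcome. Here, once dosing is over, the days that can enter the denominator stop when the pain stops, or one day later. A subject whose pain resolves early stops contributing pain-free days, and those are the days that would show the benefit.

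Two things follow. For long episodes the rate may hardly move with duration. Small accidents of recording or onset may also decide the order of two subjects. If the last pain entry is in the evening, the next morning's zero adds a pain-free day. If it is in the morning, that evening's zero falls on a day already counted as painful, and no pain-free day is added. What is at stake is how one secondary endpoint is read, and how sensitive it is.

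**Working it through.** The plan gives no figure for pain rate, so there is nothing to reproduce. The check applies the definition to the diary rule.

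**Inputs**
- K = dosing diary days: 4 from Duration of Treatment, or 5 if 20 self-started applications run into a fifth calendar day (an assumption).
- D = days with pain; k = pain-free diary days before onset; last pain day = D + k.
- c = 1 if a closing pain-free day is recorded, 0 if not.
- Plain reading (an assumption, since the term is undefined): denominator = days with a pain entry.

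**Formulas**
- Pain ends before the last dosing diary day: rate = D/K. With K = 4 and D = 1, 2, 3 this is 0.25, 0.50, 0.75, so duration is reflected properly.
- Pain reaches or outlasts the last dosing diary day: rate = D/(D + k + c).
- Fixed window, Day 1 to Day 11: rate = pain days within the window / 11.

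**Pain on every diary day from Day 1 (k = 0)**

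| D | closing day | no closing day | fixed 11 days |
|---|---|---|---|
| 5 | 5/6 = 0.83 | 5/5 = 1.00 | 5/11 = 0.45 |
| 11 | 11/12 = 0.92 | 11/11 = 1.00 | 11/11 = 1.00 |

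These values are the same for K = 4 and K = 5. More than doubling the duration moves the rate by 0.08 to 0.09, or not at all.

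**Delayed onset (k > 0)**
- Pain on Days 2 to 6 (k = 1, D = 5): 5/7 = 0.71 or 5/6 = 0.83.
- Pain on Days 3 to 6 (k = 2, D = 4): 4/7 = 0.57 or 4/6 = 0.67.

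The rate now varies more, but with onset as well as duration.

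**Order reversal**
- Five days from Day 1 without a closing day: 5/5 = 1.00. Eleven days from Day 1 with one: 11/12 = 0.92. The shorter episode scores worse.
- Closing day for both: five days from Day 1 gives 5/6 = 0.83; nine days from Day 3 gives 9/(9 + 2 + 1) = 0.75. The shorter episode again scores worse. Over the fixed window they score 5/11 = 0.45 and 9/11 = 0.82.

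**Illustrative power, rank test.** All inputs are assumed except 71 per arm: gamma durations with shape 4 and means 6 and 4.5 days, rounded and capped at 12, two-sided 5%.

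| Situation | K = 4 | K = 5 |
|---|---|---|
| Onset Day 1, closing day for all | 89% | 89% |
| Onset Day 1, closing day for a random half | 61% | 77% |
| Onset Day 1, no closing day | 63% | 77% |
| Fixed 11 days | 89% | 89% |

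With assumed onset delays of 0 to 2 days and a closing day for all, power is 65–80% over K = 4 and 5, against about 89% for the fixed window. Under other assumed durations with Day 1 onset, the loss when only half or none have a closing day runs from about 2 to about 49 points. The raw mean difference does not always shrink: with means of 4 and 3 days it is 0.09–0.14 as defined against 0.09 over the fixed window.

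**Average NRS.** With constant pain of 5 (assumed) for 4 or 10 days, the mean is 5.00 and 5.00 over pain days only, but 20/12 = 1.67 and 50/12 = 4.17 over 12 days. The choice of days matters, and the plan does not state it.

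**The case against.** The strongest reply is that pain duration is already its own endpoint. With Day 1 onset, a fixed-window rate is just min(D, 11)/11, so the recovered sensitivity is largely duration under another name. That stands, and it limits the weight of the point. It does not supply a denominator for pain rate, which is listed as an endpoint in its own right and can rank two subjects against their durations.

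A second reply is that the document calls itself a summary, so analyzable days may be defined elsewhere, and days after a recorded cessation might be meant to count. This is possible. If so, the sponsor need only point to the rule.

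A reader might infer that any pain outlasting dosing scores D/(D+1) or 1.00. The documents do not support that. Treatment may start on itching or tingling, pain-free dosing days are recorded, and they enter the denominator, so the formula needs pain on every diary day from Day 1. Nor is a rank test generally safe once every subject has a closing day; that too holds only if all pain starts on Day 1.

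**Conclusion.** The point holds in this form. On the plain reading, the pain-rate denominator depends on the outcome. For pain present from Day 1 and outlasting dosing, the rate is nearly or wholly flat in duration. With later onset it mixes onset with duration. In both cases order can reverse.

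The scores follow from the definition and the diary rule, given that reading. A power loss does not follow from the documents, which give no pain durations, no proportion of subjects with a closing day and no test. Sensitivity falls under most of the durations assumed here, but no single figure should be quoted as the trial's loss.

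It would also be too strong to call the average NRS flawed. A mean over recorded days is a valid measure of intensity; the plan only needs to say which days are averaged. Severity is minor: a secondary endpoint, with the primary endpoint and sample size unaffected.

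**What to change.** Before unblinding:
1. Compute pain rate over one common window for every subject, for example Day 1 to Day 11. Day 11 is the earliest last day, since the final assessment is "at the End of Trial Visit (Day 12±1) after initiation of treatment".
2. Count days after recorded cessation as pain-free unless pain is reported again, in the diary or at site review ("Subject diaries will be reviewed by the investigational site staff at each visit").
3. For subjects who leave while in pain, keep the full denominator and show both bounds: remaining days all painful, and all pain-free. Leaving after six days of pain from Day 1 would give 6/11 = 0.55 and 11/11 = 1.00.
4. As clarifications, state how the day of cessation is counted, which test is used, and which days enter the average NRS.

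The change is to definitions only; the date and time of cessation are already needed for the duration endpoint. The costs are that zeros after cessation are imputed although the diary does not require an entry if pain returns, that pain beyond Day 11 is truncated, and that the result overlaps heavily with pain duration.

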**Methodology:**

**Efficacy measurements:**

After self-initiation of treatment with trial medication subjects will be assessed daily for the following parameters by the Investigator until healing:

1. Lesion stage:
  - prodrome (symptoms including itching, pain, tingling, but no physical evidence of disease by inspection or by palpation in the application area),
  - erythema
  - papule (any elevation of skin without fluid in the application area)/edema,
  - vesicle (blister, fluid filled or collapsed, in the application area),
  - ulcer/soft crust,
  - hard crust,
  - residual abnormalities (residual erythema/scaling),
  - normal appearing skin.

2. Maximum lesion area (length x width) in mm^2

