**Secondary efficacy analyses**

The secondary efficacy analyses will be performed in the ITT and the PPS.

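### The pain score at the first application is not set apart from the pain-severity average or used as a baseline, which costs one secondary endpoint some efficiency

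*Combined protocol and SAP*

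**What the plan says.** Under Criteria for evaluation, Efficacy, the secondary endpoints include "Subject-assessed severity of lesion pain defined as the average daily NUMERICAL RATING SCALE (NRS) pain score", on a scale from 0 to 10. The definition excludes no score and does not say which days or entries form the average.

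Under Subject diary documentation, pain is recorded "at each application of trial treatment (at the first and last daily application as a minimum"), and afterwards "in the morning and evening on days after stop of application of trial treatment until pain disappeared". The first application of Day 1 is therefore scored even by a subject who keeps only to the minimum. The text does not say whether a score is given before or after the product is applied.

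Under Trial design, treatment is "initiated by the subject within one hour of noticing the first sign or symptom". Under Efficacy measurements, the prodrome stage is described by "symptoms including itching, pain, tingling", so a subject may start treatment with or without pain.

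On analysis, the section on secondary efficacy analyses says only this: "The secondary efficacy analyses will be performed in the ITT and the PPS". It gives no model, covariate or baseline definition for pain.

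**The concern.** A score given at the first application reflects the episode before treatment could act. Inside the outcome, it adds a component on which the arms do not differ except by chance, so the difference in average pain is pulled toward zero. Outside the outcome, the same score could explain part of the variation between subjects in later pain and so sharpen the comparison. Read literally, the plan bears the dilution and forgoes the gain, although it already collects the value.

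At stake is the sensitivity of one secondary endpoint. The silence on timing also matters: a first score is a true baseline only if it is given before the product goes on.

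**Working it through.** **The plan's own figure.** The documents give no SD, effect size, power or correlation for pain. The only sample-size figure is for the primary endpoint: 71 per arm for 26% against 50%, with 80% power and 5% type I error. Taking the test as two-sided, the continuity-corrected formula gives 72, and Fisher's exact test at 71 per arm has 79.8% power. The figure reproduces, but says nothing about pain; only n = 71 per arm is used below.

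**Step 1: weight of the first score.** Weight w = 1/(scores per day × days averaged).
- Full diary, four days (20 applications under Duration of Treatment): 1/(5 × 4) = 1/20 = 5%.
- Diary minimum, four days: 1/(2 × 4) = 1/8 = 12.5%.
- Other windows, since none is defined: 1/(5 × 8) = 2.5% for daily means over eight days; 1/(5 × 2) = 10% and 1/(2 × 2) = 25% over two days.

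If the first score carries no treatment effect, the raw difference is multiplied by 1 − w.

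**Step 2: effect on power.** Including the first score changes the SD as well as the difference, so the standardized effect is what counts. Assume that the first score and the mean of later scores have equal SD (set to 1) and correlation r. Then

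variance of the average = w² + (1 − w)² + 2w(1 − w)r

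and the standardized effect is multiplied by k = (1 − w)/√variance.

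The reference is an effect that gives 80% power when later scores alone are compared without adjustment: 2.80 × √(2/71) = 0.47 SD. Power is then Φ(2.80k − 1.96).

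| Case | r | Variance | k | Power |
|---|---|---|---|---|
| w = 1/20 | 0.3 | 0.0025 + 0.9025 + 0.0285 = 0.9335 | 0.983 | 79% |
| w = 1/20 | 0.5 | 0.0025 + 0.9025 + 0.0475 = 0.9525 | 0.973 | 78% |
| w = 1/8 | 0.3 | 0.0156 + 0.7656 + 0.0656 = 0.8469 | 0.951 | 76% |
| w = 1/8 | 0.5 | 0.0156 + 0.7656 + 0.1094 = 0.8906 | 0.927 | 74% |

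The standardized loss with full diaries is thus 1.7% to 2.7%, less than the 5% loss in the raw difference.

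**Step 3: sensitivity to the equal-SD assumption.** If first scores vary half as much as later means, full-diary power is about 79%. If nearly all first scores are zero, nothing is lost. In the other direction, if every single score has the same variance and one common pairwise correlation (0.3 to 0.7), a single first score varies more than a mean of later ones. Power is then about 76% with full diaries and 69-70% at the minimum.

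**Step 4: gain from using the score as covariate.** Adjustment multiplies the residual variance by 1 − r². Power with the first score excluded and used as covariate is Φ(2.80/√(1 − r²) − 1.96).

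| r (assumed) | Variance removed | Power |
|---|---|---|
| 0.1 | 1% | 80.4% |
| 0.3 | 9% | 84% |
| 0.5 | 25% | 90% |

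**The case against.** The strongest reply is that the document is a summary and is silent rather than wrong. It names no model for any secondary endpoint, so baseline adjustment is neither planned nor ruled out. That stands. A reader might infer that the sponsor chose to count the first score as response and rejected a baseline; the documents do not show such a choice. What remains is that the definition, applied as written, includes the score.

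Three other stronger readings also fail.
- **Bias.** A reader might infer that chance imbalance in starting pain distorts the result. Randomization balances starting pain in expectation, and the unadjusted standard error already allows for chance imbalance. Average pain over the whole episode is a legitimate outcome, so the loss is one of efficiency.
- **Large power gains.** Gains to 90% or more need r of 0.5 or above. Treatment starts within an hour of the first sign or symptom, when pain may be slight, so r could be low. At r = 0.1 adjustment gains almost nothing.
- **Stinging recorded as lesion pain.** The Safety section lists cutaneous adverse events among several signals, but nothing in the documents shows that any product stings. Superiority is tested against placebo ointment, and the comparison with Zovirax is descriptive.

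One caution also limits the remedy. Until the diary fixes the timing, the first score may follow application and is not certain to be a clean baseline.

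**Conclusion.** The point holds as a modest, inexpensive improvement to one secondary endpoint. As written, the average includes a time-zero score and the plan makes no use of it as a baseline.

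The loss in the raw difference is firm once a diary pattern is assumed and the first score is taken as unaffected by treatment. The loss in power also rests on the assumed correlation and SDs, and is only a point or two with full diaries. The precision forgone depends wholly on a correlation that the documents do not give, and may be negligible. The primary endpoint, the sample size and the validity of the randomized comparison are not affected.

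**What to change.** 1. In the diary, instruct subjects to score pain immediately before each application.
2. In the SAP, leave the first-application score out of the average, and state which days and entries the average covers.
3. Prespecify, before unblinding, an analysis of covariance of the mean of later scores with the first-application NRS as covariate.

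If the diary can no longer be changed, items 2 and 3 can still be adopted. The first score may then have been given after application, and the report of the adjusted analysis should state that limit.

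The cost is one diary instruction, one line in the SAP and one degree of freedom, with no new visit or data item.
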